1. INTRODUCTION AND BACKGROUND

Osteomyelitis (OM) and septic arthritis (SA) are relatively unusual infections in children, however, they confer considerable morbidity. At present there is limited evidence and no UK or global consensus on how to optimally treat these infections with antibiotics. The DINOSAUR study (Duration of Intravenous Antibiotic Therapy for Acute Osteomyelitis and Septic Arthritis in a Paediatric Population) has 3 components to determine the feasibility of whether a trial of shortened courses of intravenous and oral antibiotics for the treatment of bone and joint infections in children will be feasible in the UK. (www.dinosaur-study.org.uk). The feasibility study comprises a service evaluation, Delphi survey and stakeholder meeting to establish consensus from the different clinical stakeholder groups, and a qualitative study to input young people and parent's views into the Delphi and stakeholder process.

Parents were consulted during the proposal application for the DINOSAUR study and agreed that a qualitative component engaging parents of children who had had bone and joint infections would be beneficial. This qualitative study incorporates parents' views and experiences into the question of whether a formal clinical trial will be feasible.

Historically patients with OM/SA have been treated with up to six weeks intravenous antibiotics as inpatients in hospital. It is now more common practice to treat paediatric OM/SA with intravenous antibiotics initially, and then switch to oral antibiotics once clinical improvement is seen, and the child is able to take and absorb oral antibiotics. An alternative has been the use of outpatient intravenous antibiotic therapy (OPAT) before the switch to oral medicines. The criteria for switching from intravenous to oral antibiotics, and the total duration of antibiotics varies between centres within the UK and internationally.

Diagnosis of OM/SA combines haematological and biochemical blood results, microbiological analysis of blood and tissue samples and imaging using plain x-rays, ultrasound and MRI scan. Treatment may include surgery, such as drainage of a joint, and drilling and decompression, although the mainstay of treatment is immediate, intravenous antibiotic therapy.

The advantages of switching from intravenous to oral antibiotics are that the duration of hospital stay may be shortened. Additionally the risks of line-site infection and bacteraemia when a venous catheter is in place for antibiotic administration for prolonged periods are

reduced. Where used, these intravenous lines may need replacing if they become occluded or displaced necessitating hospital admission and often general anaesthetic for the procedure.

The advantage of prolonged intravenous therapy is guaranteed delivery of the antibiotic, not dependent on child or family-specific factors such as adherence or absorption. This allows more reliable treatment of invasive and potentially destructive infection.

Prolonged intravenous therapy may increase the risks of reaction to the antibiotic, and side effects such as bone marrow suppression. On the other hand, incompletely or inadequately treated bone or joint infection may rarely lead to chronic infection with destruction of cartilage, bone and growth plate, which can then cause permanent deformity and disability. However, whilst it may be desirable for many families to spend less time in hospital, with reduced duration of intravenous therapy, the perception of risks of complications secondary to potentially incomplete treatment may mean that a trial of shortened duration of antibiotics is not acceptable to parents and/or clinical stakeholders.

There has been little previous qualitative research exploring the views of paediatric patients or their parents about treatment for or the impact of acute bone and joint infections, or of the medical or surgical treatment family life during and after admission to hospital with infection in a previously healthy child. Additionally, evidence regarding patient and parent perception and understanding of risks of complications, disability or adverse effects of treatment remains anecdotal.

Importantly, the willingness of parents and patients to participate in a RCT, and what factors may influence this is not known, and will vary depending on proposed study design.

The importance of patient and family involvement (PFI) in NHS based research has become a priority at all stages of development of research projects. This qualitative study will involve patients and parents in assessing the feasibility of a future RCT, by determining their willingness to participate in a trial once specific potential study outcomes have been considered. Parents and patients may prioritise outcomes of a randomised controlled trial differently from clinicians, and this qualitative study will identify which outcomes are most important to parents and children, and where possible these can be incorporated as important outcomes to assess in a RCT.

DINOSAUR Qualitative Sub-study Team

[name] is the Chief Investigator of the DINOSAUR study as a whole and will oversee this study.

[name] is an experienced qualitative researcher and patient-public involvement lead, who will lead the qualitative methodology and supervise the qualitative researcher employed to interview young people and families.

[name], a trained qualitative researcher, who has previous experience interviewing families including children will be employed for six months to conduct the interviews and analyse the transcripts, supervised by [name]. She may be assisted by another trained and experienced qualitative researcher.

[name] is the clinical research fellow based at the Southampton NIHR Wellcome Trust Clinical Research Facility coordinating clinical aspects of the DINOSAUR trial and liaising with individual sites.

Other investigators:

[name], Professor of Paediatric Orthopaedic Surgery, Southampton

[name], Reader in Infectious Disease Epidemiology, Southampton

[name], Prof of Paediatric Infectious Diseases, St Georges London

[name], Prof of Paediatric Infectious Diseases, Oxford

[name], Prof of Paediatric Infectious Diseases, Bristol

[name], Consultant in Paediatric Orthopaedics, Newcastle

[name], Senior Lecturer in General Paediatrics, Cardiff

[name], Consultant in General Paediatrics, Norwich

[name], Consultant Paediatric Microbiologist, Sheffield

[name], Consultant in Paediatric Infectious Diseases, Liverpool

[name], Lecturer in Paediatric Infectious Diseases, Imperial College London

[name], Consultant in Paediatric Infectious Diseases, Great Ormond Street
London

[name], Consultant in Paediatric Immunology & Infectious Diseases, Birmingham
Heartlands

[name], Reader in Medical Statistics, Liverpool

2. AIMS OF STUDY

Qualitative research aims to understand: how social (including health) experiences are understood; uses methods which are sensitive to social context; and employs analytic strategies which involve an appreciation of complexity and context [1]. The research methodology employed within this study will draw on constructivist grounded theory [2]. This study aims to explore parents' and children's views, understanding and experiences of both bone and joint infections and treatment, and the parental willingness to participate in a future clinical trial.

Detailed aims:

1. To explore the experiences of parents and children treated with intravenous and/or oral antibiotic therapy for bone and joint infection about their condition and understanding about treatment
2. To identify which clinical outcomes are most important to parents and young people with bone and joint infections, in order to contribute to the wider clinical stakeholder Delphi and stakeholder consultation process.
3. To explore the views of parents and children admitted to hospital with bone and joint infections about participating in a RCT, in particular focusing on: information required in order to provide informed consent; views about and acceptability of potential interventions;

willingness to be randomised to either arm (i.e. treatment or control); influences on these factors.

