3. METHODS

Semi-structured interviews

Semi-structured interviews will be used within this study to explore the views and experiences of parents and children who have had bone and joint infections. Parents and children will be interviewed together. Semi-structured interviews are characterised by:

- an interactional exchange
- a topic centred dialogue, but with a flexible structure
- an acknowledgement that within an interview context, meaning and knowledge is co-produced [1]

The interview guides for parents and children will be developed with reference to existing literature (e.g. qualitative work in this field, factors impacting on participation in RCTs, qualitative research interviews with children); by experts in the field including our Research Fellow, [name], and in consultation with our patient and public involvement contributors. The interview guide will be piloted with between three and five children and their parents, (although as is usual practice in qualitative research, these data will be included in the final analysis).

The interviews will be digitally recorded, with permission from the families and children, all identifying features will be omitted, and the recordings will then be transcribed by a professional transcribing agency. The transcriptions will then be returned to the qualitative researcher for analysis.

Sample and Consent

A purposive sample of children aged 0 to 16 years who have had bone and joint infection within the previous year will be identified from seven centres who have participated in the main Dinosaur service evaluation. The purposive sample strategy will be developed to address variation with regard to age, gender, and ethnicity. Parents/carers, and, where appropriate and consent has been obtained, young people, will be interviewed together with their parents. We anticipate that a sample size of thirty families should be sufficient, but will

continue sampling until data saturation is reached. [3] All families approached who agree to participate will be interviewed.

Inclusion criteria

- Parents and children from 3months to sixteen-years-old with osteomyelitis and septic arthritis
- who have been treated for bone and joint infections at seven sites identified below
- who have consented to take part in this qualitative study

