1.3.4 Topic guide Children 8-12 years

CHILDREN 8-12

First section

This first bit of the interview is all about YOU and OM/SA.

1. What it was like for you when you were poorly with OM/SA? How did it make you feel?
 - What was it like staying in hospital? PROMPT on whether mum/dad etc. could stay and what that was like for them.

Second section

This part of the interview is to ask what YOU think about how the doctors found out your illness and explained it to you.

2. What did the doctors do to find out was wrong with you? (like tests or anything?)
What was that like? PROMPT for feelings, experiences.
3. How did the doctors explain the illness?
 - What was it like to learn you had this illness?
4. What treatments did the doctor talk about? (Did they talk to you as well as your mum and dad?)
 - What did you feel about them?
 - What would have happened without the treatment?

Third section

In this part I would like to ask you what it was like to have the different types of treatment for your illness.

5. Did you have to have any operations?
 - What were they for?
 - What was it like to have those/those operation? How did you feel before/after?

The type of medicine that you were given is called antibiotics and doctors gave it to you in two different ways. First of all you were given the antibiotic medicine straight into your bloodstream, through a tube which looks like this ([picture of cannula/PICC](#)), and then you were given them as a liquid like this ([show picture of oral antibiotic](#)):

6. What was it like having to have [this](#) type of antibiotic (show picture/prop of [IV antibiotic](#))
 - Can you say what was good about it and what wasn't good about it? **PROMPT:** hospital stay? Nurse giving IV? Waking at night?
7. And how about this type of antibiotic (show picture/prop of [oral antibiotic](#))?

- What was good and bad about this one? **PROMPT:** taste, remembering to take it, waking at night?
8. Why did the doctors give you this first (show IV picture) and then this? (show oral picture)
 9. Which way do you think treats the illness best?
 - PROBE which one/why? What makes you say that?
 10. Do you feel completely better from OM/SA now? (Yes/No) Why?
 11. Do mum and dad (relevant adult) think you are completely better now? Why?

Fourth section

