In this final section, I would like to ask you what you think about an idea that doctors have to compare two different types of treatments for this kind of illness, in a kind of test. This test would help doctors to find out the very best treatment for children who have bone or joint infections. As you have had already had OM/SA your opinions would be very helpful to us.

Here is a picture which explains what would happen if a family and a child are asked if they want to take part in this kind of test. SHOW PROCESS DESIGN FOR RCT 8-12 YRS and talk through it.

First of all the test I is explained to the child and their family. Then they have time to think whether they want to take part or not. If they don't want to take part that is absolutely fine. If they do want to take part, then a computer (that doesn't have any information about the child) decides WHICH treatment the child would receive. The main difference in this test is to do with how long the child would stay on IV antibiotics, that is the antibiotics given through a tube. You can see the different options in the picture.

12. Do you have any questions or comments about the test?

Let's have a look at the questions on this sheet together and see if you can answer them. Allow child to read (or read out depending on age) the questions on the sheet Process Design for RCT 8-12 years. Go through each in turn, seeking responses.

- What information would you need about the test?
- Who should give you this information?
- Who would you talk to about it?
- How would you feel about a computer deciding which treatment?
- Which treatment is better?
- Would you like to take part in this test? Why

13. Just to finish, here is a card that shows the advantages and disadvantages of staying on IV antibiotics for a long time. SHOW CARD 8-12 years. Allow child to read, or read to them.

- Having seen those, would you like to take part in this test ? *Probe reasons for any changes in/maintenance of original decision. (Explain/reassure afterwards, as necessary, that this is only a theoretical question. Not actually requesting participation.)*

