1.3.5 Topic guide Adults Version 7 15/01/2015

Adult (and 13 +) Interview guide

1. I would like to understand what it was like for you when your child first got ill with SA/OM. Could you tell me about the condition and how it affected them?
2. And please could you tell me how the condition was *diagnosed*?
3. What did you understand about:
 - a. longer term impacts of the condition?
 - b. possible complications of the condition?
 - c. the treatment options available?
 - d. and how did you feel about these?
4. Could you talk me through the different treatments that your child received (including any operations and antibiotics?) What was the order in which those treatments were given?
PROMPTS as relevant
 - a. Operation – number/ purpose?
 - b. Antibiotic – how was this administered to your child IV (drip, driver etc.)/Oral?
 - c. Location of treatment (hospital/home)

SCRIBE ON TIMELINE

“I would like to ask you in more detail about the different methods for giving antibiotics, that is intravenously (straight into the blood stream), and orally – shown on the timeline here.”

5. Could you tell me what it was like for you and your child, when **the IV antibiotics** were being administered, for (time indicated on timeline) weeks? (*e.g. ease or discomfort of treatment, experience of being in hospital etc.*)
Then (if not covered above) –
 - a. What did you understand about the clinical reasons for, or the advantages of, the use of IV antibiotics?
 - b. What were the advantages for you and your child?
 - c. What did you understand about the clinical disadvantages of using IV antibiotics?
 - d. What were the disadvantages for you and your child?
6. And could you tell me now about your child’s treatment with **oral antibiotics**? What was this part of the treatment like for you and your child? (*e.g. release from hospital, adherence etc*)
Then (if not covered above)
 - a. What did you understand about the clinical reasons for, or the advantages of, oral antibiotics?
 - b. What were the advantages for you and your child?

V7:15/10/14

Ease of use

1

- c. What did you understand about the clinical disadvantages of using oral antibiotics? What were the disadvantages for you and your child?
7. Thinking about the point when the switch was made from intravenous antibiotics to oral antibiotics – here (indicate on timeline). What was the reason for the switch being made for at that point?

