 - a. How (and by whom?) was the decision about the switch made? Did you and your child contribute to that decision?
 - b. Were you happy with the decision to switch at that point? Why?
8. Looking at the timeline, what do you think about the length of the treatment period overall?
 - a. Could it be shortened and what risks/advantages might this carry?
9. We've spoken about how you knew your child was becoming unwell. Could you tell me about any other problems/symptoms that your child experienced during the course of their illness and treatment? WHEN they happened? What did you think was causing these symptoms?
10. Could you tell me now about signs that showed you your child was getting better? What did you think was bringing about these improvements?
11. We've spoken about how your child was feeling during the course of their illness. I'd like to ask you about your feelings – could you run me through how you were feeling from when you noticed your child was getting ill, through treatment and finally to recovery?
12. How successful do you feel your child's treatment has been overall and why? (*Prompt side effects/complications*)
 - a. What are the factors that are most important to you in judging whether treatment has been successful? (PROMPTS: recovery? Time in hospital? Pain? Ease of giving treatment?)

"In this final section, I would like to ask your views about a possible clinical trial to determine the best course, combination and duration of antibiotics, for this type of infection. For this type of trial, doctors would need to recruit children with a bone/joint infection to take part. Would you mind having a read through this brief background information, and then I will ask you a few questions about it."

SHOW PROMPT BACKGROUND TO TRIAL SHEET AND TRIAL PROCESS DIAGRAM (SEE SEPARATE ATTACHMENTS)

V7:15/10/14

Ease of use

2

13. Would you mind taking a few minutes to look at this diagram? In the middle it shows the basic process that families would follow from being invited to take part in a trial through to their decision to participate or not. I would like to hear your comments about the various aspects of this process.

Then (as necessary – also referring to questions shown on RCT process sheet)

- a. Is there anything that you don't understand?
- b. Initial reactions?

WORK THROUGH QUESTIONS ON SHEET TOGETHER

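### The protocol promises children's outcome priorities, but no interview guide for ages 4 to 12 asks for them, and the question given to ages 13 and over is worded for a parent

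*Protocol*

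**What the plan says.** Two places in the protocol state the product. Section 2, aim 2, reads "To identify which clinical outcomes are most important to parents and young people with bone and joint infections", and says that this will contribute to the Delphi and stakeholder consultation. Section 1 goes further on whose views are meant: "this qualitative study will identify which outcomes are most important to parents and children". It adds that these should, where possible, become outcomes of the later randomised trial.

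Three interview guides are to deliver this. Sections 1.3.3 and 1.3.4 hold the guides for ages 4 to 7 and 8 to 12. Both ask about recovery in the same words, "Do you feel completely better from OM/SA now? (Yes/No) Why". The third guide (section 1.3.5) is headed "Adult (and 13 +) Interview guide". Its question 12a asks "What are the factors that are most important to you in judging whether treatment has been successful". The parent item directly above it, question 12, asks "How successful do you feel your child's treatment has been overall and why".

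**The concern.** A topic guide is the data collection instrument of an interview study. If an aim depends on a kind of answer that the guide does not seek from one group, that group contributes only what it happens to volunteer. Here the group is children aged 4 to 12, and the aim feeds a defined next step, the Delphi.

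Section 1 argues that parents and patients may rank trial outcomes differently from clinicians. That is the reason to collect patients' priorities directly. If few or none are collected from under-13s, an outcome list passed on as the view of parents and children would have little behind its second half, and a reader of the Delphi could not tell.

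**Working it through.** No arithmetic beyond counting applies. The check is to read each guide, question by question, against aim 2 and the matching sentence in section 1.

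**Who is in the sample.** Section 3 describes "A purposive sample of children aged 0 to 16 years who have had bone and joint infection within the previous year", with the lower limit given as 3 months in the inclusion criteria. Thirty families are anticipated, with sampling continued to saturation. Variation in age is sought, but no number per age band is given. The guides start at age 4.

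**What each guide asks.**

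| Guide | Numbered questions | Asks which outcomes matter most, or how success is judged | Nearest item |
|---|---|---|---|
| Ages 4 to 7 (1.3.3) | 13 | None | Q12: feeling fully recovered, and why |
| Ages 8 to 12 (1.3.4) | 13 | None | Q10: the same |
| Adult and 13+ (1.3.5) | 15 | Q12a, open; later Q15a, about items on a card | – |

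Across the two child guides this is 0 of 13 + 13 = 26 numbered questions. Question 12a appears in 1 guide of 3.

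**Could the nearest child items stand in?**

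- The recovery question records present state and the child's reason for it. A reason may reveal one outcome that the child notices, but it does not ask what counted most.
- The good-and-bad questions about intravenous and oral antibiotics concern the experience of each route.
- The question on which route works better concerns perceived efficacy.
- The 8-12 guide has a closing section on the possible trial, with items such as "What information would you need about the test". It covers information, the computer's allocation, treatment preference and willingness to join. The child then sees a card (section 1.3.2) that mentions long-term problems and disability. The question that follows is about willingness to take part, not about which item on the card matters.

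So aim 3, on trial participation, has its own section in the 8-12 guide. Aim 2 has no item in either child guide.

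**Ages 13 to 16.** The heading of section 1.3.5 assigns them the adult guide, and so question 12a. But question 12, which introduces it, asks about the respondent's child, and the guide speaks to a parent throughout. No alternative wording for a teenager is shown. Since section 3 has parents and children interviewed together, the question as worded invites the parent's answer first.

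**The case against.** The case on the other side has real force, and several stronger readings fail against it.

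- A reader might infer that the Delphi would receive parents' views only. The protocol does not support that. Those aged 13 to 16 are assigned question 12a, and aim 2 itself speaks of young people, which may mean that group. The mismatch for ages 4 to 12 is with the wording of section 1, which says children.
- A reader might infer that the child guides ignore outcomes. They do not: both ask about recovery with a reason, and about good and bad sides of each treatment. What is absent is any question on importance.
- A reader might infer that question 12a steers parents to its four prompts (recovery, hospital time, pain, ease of giving treatment). It is an open question with prompts in brackets. Question 12 also prompts for side effects and complications, and question 15a asks which items on a card would be important to the family. That card names chronic infection and permanent disability.
- The method is flexible. Interviews are semi-structured, families are interviewed together, the guide is piloted with three to five children and their parents, and a grounded-theory analysis can draw priorities out of accounts of experience. A skilled interviewer would probably reword question 12 for a teenager.

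The first three points stand and limit the finding. The fourth stands in part. Flexibility permits probing, but the child guides give no cue to probe for what matters most, so whether it happens would depend on the interview. Priorities inferred from experience are weaker evidence than an answer to the question.

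**Conclusion.** The point holds in a limited form. As written, the guides seek no direct answer on outcome priorities from children aged 4 to 12, although section 1 promises the outcomes most important to children. For ages 13 to 16 the question exists but is put as a parent's question. Children's contribution to aim 2 would therefore rest on a number of teenagers that the protocol does not state and on indirect answers from younger children.

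This assumes that interviewers follow the printed guides and that no separate wording for teenagers exists outside the protocol. It does not make aim 2 unreachable, and the parents' side is adequately covered. It is worth correcting because the change is small and bears directly on one of three stated aims.

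**What to change.** 1. In the 8-12 guide, after the two questions on whether the child and the parents think recovery is complete (Q10 and Q11), add one open question, for example: when you were getting better, what mattered most to you? Put a simple form of it, using the toy, after the matching questions (Q12 and Q13) in the 4-7 guide.
2. In the adult and 13+ guide, add a version of questions 12 and 12a in which the young person speaks about their own treatment, and cue the interviewer to put it to them as well as to the parent.
3. If the child guides are not changed, limit the section 1 statement to parents and those aged 13 and over. The wording in item 2 would still be needed, since that statement would then depend on it.

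The cost is a few minutes per interview and a minor amendment. The very youngest respondents may give thin answers, but that would at least be recorded.
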